1. LIST OF ABBREVIATIONS

1L	First line
2L	Second line
3L	Third line

BI Boehringer Ingelheim

CDC Center for Disease Control and Prevention Center

CI Confidence Interval CRF Case report form

CSCO Chinese Society of Clinical Oncology

DDLPS Dedifferentiated liposarcoma

ECOG Eastern Cooperative Oncology Group

EMPI Enterprise Master Patient Index

EMR Electronic medical records

GPP Good Pharmacoepidemiology Practice

HCRU Healthcare resource utilization IEC Independent Ethics Committee

IQR Interquartile range KM Kaplan-Meier LOT Line of therapy

NATDSS National Anti-Tumor Drug Surveillance System

NCC National Cancer Center

NCCN National Comprehensive Cancer Network

NIS Non-Interventional Study

ONIS Observational and Non-Interventional Study

OS Overall survival

SAS Statistical Analysis System

SD Standard deviation

SEAP Statistical and Epidemiological Analysis Plan

SOP Standard operating procedure

3. PURPOSE AND SCOPE

This ONIS is conducted based on existing database. This document provides an overview of the processes and procedures of data quality review and management, methods used to describe, analyze and display data, and quality control of data throughout the conduct of ONIS.

4. AMENDMENTS AND UPDATES

Not applicable.

5. RESEARCH QUESTION AND OBJECTIVES

Primary objective:

To describe the overall survival (OS) of Chinese unresectable locally advanced or metastatic dedifferentiated liposarcoma (DDLPS) patients

Secondary objective:

To describe the treatment patterns of Chinese DDLPS patients

Exploratory objective:

To describe demographic, clinical characteristics and treatment outcomes of Chinese DDLPS patients

To describe the direct medical cost and healthcare resource utilization of Chinese DDLPS patients

6. RESEARCH METHODS

6.1 STUDY DESIGN

This will be a non-interventional/observational study of Chinese DDLPS patients using existing data curated by . No BI product will be studied, and no new interventions or procedures will be performed.

The primary outcome is OS. Secondary outcomes include survival after initial diagnosis, and treatment patterns. Exploratory outcomes may include patient demographics, clinical characteristics, duration of treatment (DOT), time to next treatment (TTNT) by lines,

Statistical and Epidemiological Analysis Plan (SEAP) for Observational and Non-Interventional Studies (ONIS)

Page 5 of 36

healthcare resource utilization and direct medical cost, etc. None of the outcomes reflect safety issues.

6.2 SETTING

In this study, patient data from NATDSS network from January 1, 2013 to December 31, 2022 will be used. Details of data source are described in section 8.

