6.3 STUDY POPULATION

Inclusion criteria:

- Patient has two or more documented clinical visits in the National Anti-Tumor Drug Surveillance System (NATDSS) network on or after January 1, 2013.
- Patient has a confirmed diagnosis of DDLPS during his/her lifetime.
- At least 18 years old at the date of initial diagnosis

No exclusion criteria are applied.

Eligible population will be divided into two groups:

- Cohort 1 will include unresectable locally advanced or metastatic DDLPS patients who received at least one line of systemic antineoplastic treatment by the end of cohort identification period (index date = start date of first line (1L) treatment).
- Cohort 2 will include patients with DDLPS who have not initiated 1L systemic antineoplastic treatment by the end of cohort identification period (index date = date of initial DDLPS diagnosis during cohort identification period). Patients initiated 1L treatment afterwards or patients received adjuvant and/or neoadjuvant therapy only through follow-up will be included in Cohort 2.

In both cohorts, 1L therapy will be defined as the initial set of drugs used after unresectable locally advanced or metastatic diagnosis. Metastatic patients will be defined as those with metastatic diagnosis or presence of metastatic sites; unresectable locally advanced patients will be defined as those with advanced diagnosis and without subsequent surgical resection.

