6.4 STUDY VISITS

Definitions of relevant time periods are detailed below.

Study period: January 1, 2013 – December 31, 2022

Baseline period: All available data prior to index date

Cohort identification period: January 1, 2013 – December 31, 2021 (one year before end of study period)

[figure not shown]
Statistical and Epidemiological Analysis Plan (SEAP) for Observational and Non-Interventional Studies (ONIS)

Index date: The index date for Cohort 1 will set to the date of initiation of 1L treatment; the index date for Cohort 2 will be the date of initial DDLPS diagnosis during cohort identification period.

Follow-up period: From index date until date of death, if available, or the date of censoring if there is no record of death, whichever occurs first. For survival and treatment patterns, the date of censoring will be the last activity date, defined as the date of the last visit of any type prior to the end of the study period.

Figure 1 illustrates the time periods for the study timelines.

(a). Cohort 1

(b). Cohort 2

[figure not shown]

Figure 1. Overall study period

Abbreviations: 1L = first line

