10.1.2 Analysis of secondary objectives

Survival after initial diagnosis will be estimated by the KM method to obtain median estimates with 95% CIs and IORs for Cohort 1 and Cohort 2.

Treatment patterns for Cohort 1 and Cohort 2 will be described by the number of lines, count with percentage (%) of patients by treatment lines, type of therapy and therapy regimens in each line.

LOTs are defined by the temporal relationship and sequencing of treatment regimens by using the dates of initiation and discontinuation of chemotherapy, targeted therapy, and/or immunotherapy. For each patient, 1L treatment regimen is defined as the first systemic treatment of any chemotherapy, and/or targeted drugs given to a patient after advanced or metastatic DDLPS diagnosis. A treatment line is advanced to the next line when a patient initiates new combinations of drugs or has the evidence of progression of disease. The start date of each LOT is defined as the date of initiation of new regimen, and the end date of each LOT is defined as the date of last dose prescribed or recorded at/before discontinuation.

Statistical and Epidemiological Analysis Plan (SEAP) for Observational and Non-Interventional Studies (ONIS)

Page 18 of 36

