ANNEX 2. MOCK TABLE AND FIGURE

The following figures and tables will be developed for analyses of primary, secondary and exploratory objectives and will be replicated for subgroup analyses and sensitivity analyses, pending feasibility.

Table 1. Patient baseline demographic characteristics for Cohort 1 and Cohort 2

Demographic characteristics	Cohort 1	Cohort 2
Number of patients, N		
Index year, N (%) 2013		
2014		
2015		
2016		
2017		
2018		
2019		
2020		
2021		
Age at initial diagnosis, years		
$Mean \pm SD$		
Median (IQR)		
Min, Max		
Missing / Unknown		
Age (categorized) at initial diagnosis, N (%)		
<65		
≥65		
Missing / Unknown		
Age at index, years		
$Mean \pm SD$		
Median (IQR)		
Min, Max		

Statistical and Epidemiological Analysis Plan (SEAP) for Observational and Non-Interventional Studies (ONIS)

Page 21 of 36

Demographic characteristics	Cohort 1	Cohort 2
Missing / Unknown		
Age (categorized) at index, N (%)		
<65		
≥65		
Missing / Unknown		
Sex, N (%)		
Female		
Male		
Missing / Unknown		
Insurance type, N (%)		
National medical insurance		
Commercial insurance		
Out of pocket		
Others		
Missing / Unknown		
Region, N (%)		
Eastern China		
Central China		
Western China		
Northeast China		
Missing / Unknown		

Abbreviations: N = number; SD = standard deviation; IQR = interquartile range; min = minimum; max = maximum

Notes: Eastern China includes Beijing, Tianjin, Hebei, Shanghai, Jiangsu, Zhejiang, Fujian, Shandong, Guangdong, and Hainan; central China includes Shanxi, Anhui, Jiangxi, Henan, Hubei, and Hunan; western China includes Inner Mongolia, Guangxi, Chongqing, Sichuan, Guizhou, Yunnan, Tibet, Shaanxi, Gansu, Qinghai, Ningxia, and Xinjiang; northeast China includes Liaoning, Jilin, and Heilongjiang.

Statistical and Epidemiological Analysis Plan (SEAP) for Observational and Non-Interventional Studies (ONIS)

Page 22 of 36

Table 2. Patient clinical characteristics for Cohort 1 and Cohort 2

Clinical characteristics	Cohort 1	Cohort 2
Number of patients, N Year of initial diagnosis, N (%)		
Before 2013		
2013		
2014		
2015		
2016		
2017		
2018		
2019		
2020		
2021		
Missing / Unknown		
Disease stage at initial diagnosis, N (%)		
0		
I		
II		
III		
IV		
Missing / Unknown		
Histology, N (%)		
Dedifferentiated		
Other		
Missing / Unknown		
ECOG performance status, N (%)		
0		
1		
2		
3		
4		
Missing / Unknown		

Statistical and Epidemiological Analysis Plan (SEAP) for Observational and Non-Interventional Studies (ONIS)

Page 23 of 36

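### Cohort 1 has no new-user rule at the 1 January 2013 data start, so patients already treated for advanced disease can get a late index date or a later line labelled 1L

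*SAP*

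**What the plan says.** SAP 6.2 fixes the data window: "patient data from NATDSS network from January 1, 2013 to December 31, 2022 will be used". SAP 6.3 and protocol 9.2.2 then set three entry conditions. Besides adult age at initial diagnosis, they are "Patient has two or more documented clinical visits in the National Anti-Tumor Drug Surveillance System (NATDSS) network on or after January 1, 2013" and "Patient has a confirmed diagnosis of DDLPS during his/her lifetime". Both documents add: "No exclusion criteria are applied".

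Cohort 1 must have received at least one systemic line by the end of the identification period (31 December 2021), which is an upper limit only. The Cohort 2 index diagnosis, by contrast, must fall inside that period.

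For both cohorts "1L therapy will be defined as the initial set of drugs used after unresectable locally advanced or metastatic diagnosis". SAP 10.1.2 repeats the idea for line numbering: "1L treatment regimen is defined as the first systemic treatment of any chemotherapy, and/or targeted drugs given to a patient", again after the advanced diagnosis. SAP 6.4 ties time zero to it: "The index date for Cohort 1 will set to the date of initiation of 1L treatment". SAP 10.1.1 measures OS from the same date.

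The baseline period (SAP 6.4) is whatever data exist before the index date, with no minimum length. Mock Table 1 in SAP Annex 2 begins at "Index year, N (%) 2013" and ends at 2021. Mock Table 2 has a row for initial diagnosis before 2013. The visible text has no washout, no treatment-free look-back and no rule for drugs given before 2013.

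**The concern.** Calling a regimen first-line needs evidence that nothing came before it. For a patient whose advanced disease began before the data do, there are two cases, and the plan covers neither.

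- **Earlier drugs not in the data.** The first recorded regimen meets the 1L definition by default. If the patient is still on true 1L, the regimen and line number are right but the start date is late. If the patient is already on 2L or later, the regimen is also wrong and every later line number is too low.
- **Earlier drugs visible.** The true 1L date precedes 2013 and has no place in mock Table 1. The two-visit criterion also means the patient is counted only because he or she survived into 2013.

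At stake are the index date of the primary outcome, the treatment patterns that form the secondary objective (mock Tables 5 and 6), the timing results in mock Tables 7 and 8, and the subgroup in protocol 9.7.4 defined by doxorubicin as 1L. Protocol section 12 says the results may supplement regulatory submissions.

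**Working it through.** **1. The protocol's own model.** Protocol 9.5 assumes uniform entry, exponential OS with median m = 8, 10 or 12 months, and about 20% type I censoring. It states 95% CIs for the median. With no censoring before the median, the log-log limits t solve ln(t/m) = ±1.96 × √[(1−S)/(nS)] / (−ln S), where S = 0.5^(t/m).

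| n = 1000, m | Protocol | Recomputed |
|---|---|---|
| 8 | 7.287, 8.764 | 7.296, 8.728 |
| 10 | 9.100, 10.972 | 9.121, 10.910 |
| 12 | 10.916, 13.175 | 10.945, 13.092 |

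All 12 rows agree to within about 1.3% per bound. The model is therefore as described, and the yardstick at m = 10 is a half-width of (10.972 − 9.100)/2 ≈ 0.94 month.

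**2. Share of Cohort 1.** Two assumptions are added: incidence before 2013 equals that after, and a fraction f of patients alive on 1 January 2013 with an earlier 1L have a later drug record and no visible earlier one. In a steady state, the number alive equals the entry rate times mean OS, and mean OS = m/ln 2. The identification period is 108 months.

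Share = f × (m/ln 2) / [f × (m/ln 2) + 108]

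| m | Mean OS (months) | f = 0.25 | f = 0.5 | f = 1 |
|---|---|---|---|---|
| 8 | 11.54 | 2.6% | 5.1% | 9.7% |
| 10 | 14.43 | 3.2% | 6.3% | 11.8% |
| 12 | 17.31 | 3.9% | 7.4% | 13.8% |

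The pre-COVID sensitivity analysis in protocol 9.7.5 shortens identification to 84 months. The same formula then gives 12.1-17.1% for f = 1 and 6.4-9.3% for f = 0.5. That analysis concentrates these patients and does not remove them.

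**3. Effect on median OS.** This was simulated at a true median of 10 months with f = 0.5 and f = 1. The Weibull shapes are assumptions.

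| Hazard | Shift in median OS (months) |
|---|---|
| Falling (shape 0.7) | +0.7 to +1.3 |
| Constant (exponential, as in the protocol) | about 0 |
| Rising (shape 1.5) | −0.2 to −0.3 |

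The near-zero result is expected, because residual survival under an exponential has the same distribution as survival from 1L.

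**4. Late date versus wrong line.** A three-line model was run with every input assumed: mean line durations of 4-6, 3-4 and 2-3 months, a 50-60% chance of a further line, mean survival of 6-9 months after the last line, and patients counted if on drug on 1 January 2013. It gave 5-8% of Cohort 1 with a late index date (median delay about 4-6 months), about 2-3% with a later line labelled 1L, and a shift in median OS of about −0.1 month.

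**The case against.** The strongest reply is that no passage tells the analyst to call the first drug seen in 2013 1L. The definition refers to the first drugs after the advanced diagnosis, the baseline takes all available earlier data, and mock Table 2 expects some older history. On that view a recorded 2011 start would be noticed and set aside. This stands in part: mislabelling follows only where earlier treatment is invisible, and the documents do not say how often that is. It does not supply the missing rule for either case.

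Several stronger readings are tempting but not supported:

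- **The row for diagnosis before 2013 proves the error.** It refers to initial diagnosis. A patient with localised disease in 2010 who starts 1L in 2015 belongs there and is correctly indexed.
- **About half of index year 2013 is affected.** Replacing 108 by 12 in the formula gives 49-59% at f = 1, but only if every such patient has a further drug record, all of those records fall in 2013, and no earlier treatment is visible. The database was established in 2018, so full capture in 2013 is itself uncertain.
- **The primary median is materially biased.** Under the protocol's own survival model it is not. Other hazard shapes are assumptions from outside the documents.
- **All line numbers are shifted.** A patient still on true 1L keeps the right regimen and number.

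Redaction also matters. The exploratory variables, SAP 10.2 and the timeline figure are not visible and could hold a prior-treatment rule. The visible mock tables show none. The limitations section (protocol 9.9) mentions treatment misclassification in general, but not the 2013 data start.

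**Conclusion.** The gap is real: the visible plan does not make Cohort 1 a new-user cohort, and neither sensitivity analysis in protocol 9.7.5 removes the patients concerned. Its size cannot be read from the documents. Under uniform entry, exponential OS with medians of 8-12 months and equal incidence before 2013, 9.7-13.8% of Cohort 1 is a ceiling and about 5-7% applies if half have a later drug record, concentrated in the earliest index years. A falling hazard would leave more long survivors and raise that ceiling.

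For median OS, the size and direction of any bias depend on the hazard shape: about nil under the protocol's model, and comparable with the CI half-width at n = 1000 if the hazard falls. The firmer consequence is for 1L regimen, number of lines, time from diagnosis to 1L, treatment duration and membership of the 1L-doxorubicin subgroup. This should be corrected before analysis, but it does not by itself invalidate the primary estimate.

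**What to change.** In SAP 6.3 and protocol 9.2.2, require for Cohort 1 that:

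1. the 1L start falls between 1 January 2013 and 31 December 2021; and
2. there is no record or history of systemic treatment for advanced disease before it, shown either by a first advanced diagnosis inside the patient's observed data or by a stated treatment-free look-back in those data.

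Report the patients removed as a separate count. Add a sensitivity analysis of OS and mock Tables 5-8 that leaves out the earliest index years, for example 2013-2014.

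A calendar limit on the advanced diagnosis alone would not be enough. If records begin in 2013, a previously treated patient's first recorded advanced diagnosis may also be dated 2013, and the patient would pass. Such a limit would also drop genuine new starters whose advanced diagnosis is older. Tying the condition to each patient's observed data also covers hospitals whose records begin later than 2013.

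The cost is a few lines of eligibility text, one count and one repeated set of tables. There is a modest loss of patients, mostly in early index years, including some true new starters with an older advanced diagnosis or a short recorded history.

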6.3 STUDY POPULATION

Inclusion criteria:

- Patient has two or more documented clinical visits in the National Anti-Tumor Drug Surveillance System (NATDSS) network on or after January 1, 2013.
- Patient has a confirmed diagnosis of DDLPS during his/her lifetime.
- At least 18 years old at the date of initial diagnosis

No exclusion criteria are applied.

Eligible population will be divided into two groups:

- Cohort 1 will include unresectable locally advanced or metastatic DDLPS patients who received at least one line of systemic antineoplastic treatment by the end of cohort identification period (index date = start date of first line (1L) treatment).
- Cohort 2 will include patients with DDLPS who have not initiated 1L systemic antineoplastic treatment by the end of cohort identification period (index date = date of initial DDLPS diagnosis during cohort identification period). Patients initiated 1L treatment afterwards or patients received adjuvant and/or neoadjuvant therapy only through follow-up will be included in Cohort 2.

In both cohorts, 1L therapy will be defined as the initial set of drugs used after unresectable locally advanced or metastatic diagnosis. Metastatic patients will be defined as those with metastatic diagnosis or presence of metastatic sites; unresectable locally advanced patients will be defined as those with advanced diagnosis and without subsequent surgical resection.

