7. VARIABLES

The analysis will be descriptive only, and there are no *a priori* hypotheses. There will be no prespecified exposures or covariates to be used as the basis for formal statistical testing and for *a priori* comparison of groups.

Statistical and Epidemiological Analysis Plan (SEAP) for Observational and Non-Interventional Studies (ONIS)

Page 7 of 36

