7.1.2 Secondary outcomes

Survival after initial diagnosis

Outcome type: Secondary

• Outcome name: Survival after initial diagnosis

• **Time frame**: Time from initial diagnosis until the earliest record of death or end of the study period

• **Population**: Cohort 1, Cohort 2

Survival after initial diagnosis for each patient will be defined as the date of death minus the date of initial diagnosis. For patients with no record of death, survival after initial diagnosis will be censored at the last activity date before the end of the study period.

Description of treatment patterns

Outcome type: Secondary

• Outcome name: Treatment patterns

• Time frame: Treatment patterns are assessed at the index date and during follow-up

■ **Population**: Cohort 1, Cohort 2

The following variables of interest will be assessed to describe treatment patterns defined by LOT and regimens.

Treatment patterns by LOT and regimens

Variable	Definition	Timing
1L Treatment Type	Regimen name from LOT data for treatments with line number = 1, 2 and 3. Treatment	Any time after
2L Treatment Type	types will be classified as follows, specific treatments and categories may change upon examination of the data:	index date
3L Treatment Type		

Statistical and Epidemiological Analysis Plan (SEAP) for Observational and Non-Interventional Studies (ONIS)

[figure not shown]
Variable	Definition	Timing
	NCCN/CSCO preferred	
	 Doxorubicin 	
	 Epirubicin 	
	 Liposomal doxorubicin 	
	AD (doxorubicin, dacarbazine)	
	 AIM (doxorubicin, ifosfamide, mesna) 	
	Ifosfamide, epirubicin, mesna	
	 Larotrectinib (NTRK fusion pos sarcomas only) 	
	 Entrectinib (NTRK fusion pos sarcomas only) 	
	 Pazopanib 	
	• Eribulin	
	Trabectedin	
	Other	
	 AD LMS only (doxorubicin, dacarbazine) 	
	Gemcitabine and docetaxel	
	Gemcitabine	
	Gemcitabine and vinorelbine	
	Gemcitabine and dacarbazine	
	 Dacarbazine 	
	 Ifosfamide 	
	Temozolomide	
	Vinorelbine	
	 Regorafenib 	
	 MAID (mesna, doxorubicin, ifosfamide, dacarbazine) 	
	 Pembrolizumab 	
	 durvalumab 	
	• Other	
Total number of treatment lines	From LOT data, for all lines after index date, categorical variable defined as total of treatment lines reported.	Any time after index date
Concurrent steroid therapy	Any record of a drug classified as a corticosteroid.	Anytime from the start to end of 1L, 2L, or 3L

Statistical and Epidemiological Analysis Plan (SEAP) for Observational and Non-Interventional Studies (ONIS)

Page 9 of 36

Variable	Definition	Timing

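### Survival after initial diagnosis is estimated from diagnosis in two cohorts defined by later first-line treatment, so neither curve estimates survival after diagnosis in DDLPS patients overall

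*SAP*

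**What the plan says.** **Time origin.** SAP 7.1.2 starts the clock at diagnosis: "Survival after initial diagnosis for each patient will be defined as the date of death minus the date of initial diagnosis". Protocol 9.3.1.2 agrees. Both give the population as Cohort 1 and Cohort 2.

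**Groups.** Under SAP 6.3, Cohort 1 holds unresectable locally advanced or metastatic patients who had 1L by 31 December 2021. The complement is set the same way: "Cohort 2 will include patients with DDLPS who have not initiated 1L systemic antineoplastic treatment by the end of cohort identification period". SAP 6.3 adds: "Patients initiated 1L treatment afterwards or patients received adjuvant and/or neoadjuvant therapy only through follow-up will be included in Cohort 2". In both cohorts, 1L is counted only after unresectable locally advanced or metastatic disease has been diagnosed.

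**Estimator.** SAP 10.1.2: "Survival after initial diagnosis will be estimated by the KM method to obtain median estimates with 95% CIs", for each cohort, as in protocol 9.7.2. Mock Table 4 has two columns, one per cohort, with the median, IQR and survival at 6, 12, 18 and 24 months. The Figure 2 caption names both cohorts.

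**Entry rules.** Eligibility requires this: "Patient has two or more documented clinical visits in the National Anti-Tumor Drug Surveillance System (NATDSS) network on or after January 1, 2013". SAP 6.4 says "the index date for Cohort 2 will be the date of initial DDLPS diagnosis during cohort identification period", while mock Table 2 has a row for diagnoses before 2013.

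**Aim.** SAP 5 includes, as exploratory, "To describe demographic, clinical characteristics and treatment outcomes of Chinese DDLPS patients". SAP 7 states: "The analysis will be descriptive only".

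**The concern.** A survival curve from diagnosis should group patients by what was known at diagnosis. Here the group depends on what happened afterwards. Nobody in Cohort 1 can die between diagnosis and 1L, because such a death would have put the patient in Cohort 2. Cohort 2 takes those early deaths. It also takes patients with a good outlook who never needed 1L, and patients diagnosed too late in the window to have started it.

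The two curves can therefore separate even when every patient has the same risk of death and 1L does nothing. The limitations in protocol 9.9 cover death under-capture, missing data, generalisability and COVID-19, but not this.

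At stake is how the secondary result is read. Protocol 7 says the Chinese authority recommended collecting real-world survival data to support a New Drug Application, and protocol 12 allows the results to supplement submissions. A by-cohort median could be taken as the natural history of DDLPS from diagnosis.

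**Working it through.** **The plan's own figure.** The documents give no expected value for survival after diagnosis. Their only computed figures are the intervals for median OS from 1L in protocol 9.5. These reproduce: for N = 300 and median 8 months, simulated KM with a log-log interval and 20% censoring gives 6.687 to 9.404, against 6.732 to 9.435. They concern the primary outcome and do not bear on this point.

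**Inputs.** From the documents: diagnosis between January 2013 and December 2021 (108 months), cohort split at month 108, study end at month 120. Assumed, because the documents are silent: survival from diagnosis, time to 1L and disease extent at diagnosis.

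**Step 1: shared hazard, closed form.** Let death have rate λ = ln 2/24 = 0.0289 per month and 1L rate μ = ln 2/6 = 0.1155, independent, with no treatment effect. Ignoring the calendar cut-off:

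- Share reaching 1L before death: μ/(λ+μ) = 0.80.
- Cohort 1: S₁(t) = [(λ+μ)e^(−λt) − λe^(−(λ+μ)t)]/μ = 1.25e^(−λt) − 0.25e^(−(λ+μ)t). Median 31.5 months; S₁(6) = 0.946; S₁(24) = 0.617.
- Cohort 2: S₂(t) = e^(−(λ+μ)t). Median ln 2/(λ+μ) = 4.8 months.
- Pooled: 0.80·S₁ + 0.20·S₂ = e^(−λt), which is the true curve with median 24.

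**Step 2: add the calendar rules.** Patients diagnosed late and untreated at month 108 move to Cohort 2. Simulation of 400,000 patients (error about 0.1 month) gives:

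| | Cohort 1 | Cohort 2 | Pooled |
|---|---|---|---|
| Median, months | 31.1 | 6.8 | 24.1 |
| 6-month survival | 94% | 53% | 84% |
| 24-month survival | 61% | 15% | 50% |

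The Cohort 1 excess depends on the wait. With a 1-month median to 1L it reads 13.4, 25.4 and 37.5 against true medians of 12, 24 and 36 (+12%, +6%, +4%).

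**Step 3: add case mix.** Step 1 lets everyone start 1L from diagnosis, which SAP 6.3 does not. Now let some patients start with localised disease and become eligible for 1L only once advanced, with a 10-month median from that point (the middle of the 8, 10 and 12 that protocol 9.5 assumes from 1L). The median time to advanced disease is 18 months; patients who never progress have an assumed median of 120 months.

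| Localised at diagnosis | Median from advanced disease to 1L, months | All patients | Cohort 1 | Cohort 2 |
|---|---|---|---|---|
| 30%, all progress | 6 | 14.8 | 18.9 | 8.5 |
| 30%, all progress | 1 | 14.7 | 14.6 | not tabulated |
| 70%, half never progress | 2 | 32.6 | 19.8 | 84.0 |

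(The 14.8 and 14.7 differ only by simulation error.) Over 36 such settings the Cohort 1 median ran from 55% below to 28% above the all-patient median. In the last row, 47% of Cohort 1 and 90% of Cohort 2 had localised disease at diagnosis, so much of that gap is real difference in disease extent.

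**Step 4: two-visit rule in a pooled curve.** If the second visit falls after diagnosis, survival to it is also guaranteed. With that visit uniform over the first 1 to 6 months (assumed), for all patients or half of them, true medians of 12, 24 and 36 read 12.3–14.9, 24.3–27.0 and 36.4–39.1. With late entry at the second visit they read 12.0–12.1, 23.9–24.1 and 36.0–36.2.

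**The case against.** **The plan delivers what it declares.** The outcome states its population as the two cohorts, the objective naming treatment outcomes in DDLPS patients is exploratory, and comparison between groups is disclaimed. A reader might infer that the plan promises one overall survival-from-diagnosis figure and fails to give it. No visible text makes that promise. What remains is that an outcome called survival after initial diagnosis will be read as such, and neither cohort's figures support that reading. The descriptive label removes a test, but the medians and rates are themselves the result.

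**The illustrations are assumption-driven.** This stands. Step 1 ignores the advanced-disease requirement for 1L, and Step 3 mixes conditioning with true case mix. Other assumed mixes bring the medians close together: 23.1 and 21.6 against 22.4 overall. A reader might infer that Cohort 1 survival must be overstated, or by a known amount. The documents support neither.

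**The pooled analysis may exist elsewhere.** SAP text between 10.1.2 and 10.3 and the figures are not shown, so one can say only that no pooled curve is visible. Subgroup outputs are planned, but protocol 9.7.4 places them within cohorts, so they keep the conditioning.

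**The entry points are soft.** The two-visit rule does not require visits after diagnosis, and the Cohort 2 index wording could mean the first diagnosis recorded in the window. Both stand, so late entry is proposed as a sensitivity analysis and pre-2013 diagnoses are simply left out of the pooled curve.

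**Conclusion.** The concern holds as a matter of definition: the clock starts at diagnosis and the groups are formed by later 1L status. The by-cohort medians, IQRs and 6- to 24-month rates describe groups selected on future events. They should not be compared, and neither should be quoted as survival after diagnosis in Chinese DDLPS patients.

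Confidence is high in the mechanism and low in its size. The 31, 7 and 24 months rest on a shared exponential hazard, a true median of 24 months, a 6-month median to 1L and 1L being open to everyone from diagnosis. Under assumed case mix, Cohort 1 may be high, low or nearly right.

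A reader might also infer that the primary result is biased in the same way. It is not: OS in Cohort 1 starts at 1L. Treatment patterns by cohort are likewise untouched. The point should be fixed before analysis, but it does not threaten the primary objective.

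**What to change.** In SAP 10.1.2, mock Table 4 and Figure 2, with protocol 9.3.1.2 and 9.7.2 aligned:

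1. Add one KM estimate of survival after initial diagnosis in all eligible patients first diagnosed from 1 January 2013 to 31 December 2021, both cohorts pooled, and name it as the estimate for DDLPS patients overall.
2. Add a sensitivity analysis in which time at risk starts at the second qualifying visit when that visit follows diagnosis.
3. Keep the by-cohort results, labelled as conditional on later 1L status and not comparable between cohorts.
4. Optionally, split the pooled curve by disease stage at initial diagnosis where recorded. Mock Table 2 already lists it, and it is fixed at time zero.

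**Cost.** One extra curve and table column, one sensitivity run, and wording changes; the protocol change goes to the IRB/IEC under protocol 10.1. No new data are needed. Late entry slightly widens the early intervals. The pooled estimate still depends on the mix of disease extent at diagnosis and on incomplete death capture, which protocol 9.9 puts at possibly 80%, so it should carry those caveats.
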